10.3.2 Primary analysis

The main analysis will focus on the objective response rate (ORR) of the P Cohort.

An objective response is defined as either a CR or PR assessed, as outlined in sections 9.1.3 and 10.3.1 (iEE population), first by RECIST 1.1 and then by iRECIST criteria at the discretion of the local Investigator.

Best objective response of either type will be centrally confirmed using the [Quibim Precision[®]](#) software (the cloud-based repository for radioimaging). In case of disagreement between local and central evaluation, the central response evaluation will be used for the analysis. The duration of response will be calculated accordingly.

An estimate of ORR and its 95% CIs will be calculated using the Clopper-Pearson method. Discrepant results, impinging in the acceptance of rejection of the null hypothesis, will be discussed and agreed upon between the Protocol Chair and the Sponsor.

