10.0 STATISTICAL CONSIDERATIONS

10.1 General considerations

The hypothesis tested by ARETHUSA is whether immunoediting in MMR proficient cancers can be disrupted by increasing the tumor mutational load with TMZ, enabling the tumor to dynamically express neo-antigens that positively affect T cell functions under check-point inhibition.

The main analysis thus will concern the response to pembrolizumab in MMR proficient patients (cohort P) with measurable disease at baseline who have received at least 1 cycle of pembrolizumab (iEE population, see 10.3.1).

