10.2 Sample size calculation

A two-stage Green-Dahlberg design has been used [Green SJ and Dahlberg S Statistics in Medicine 11:853-862,1992], to calculate the sample size for the **P-cohort** under the following assumptions:

- The null hypothesis that the true (H_0) response rate is 10% (not considered clinically compelling) will be tested against a one-sided alternative (H_1).
- In the first stage, 10 patients will be accrued. If no responses are observed, the study will be stopped. Otherwise, 10 additional patients will be accrued for a total of 20.
- The null hypothesis will be rejected if 5 or more responses are observed in 20 patients.
- This design yields a type I error rate of .05, and power of 90% when the true response rate is 40%.
- In order to recruit 20 patients in the P-cohort the number of MMR unselected patients to be pre-screened for MMR status MGMT promoter methylation and the number of MGMT-PM+ to be primed with TMZ are reported in Table 10.1. below as well as in Study Diagram, section 4.2.

Table 10.1 Number of patients required in each trial Phase.

Number of Patients to be:	N	Expected Percent
RAS mut MMR proficient cases to be screened	670	A
expected MGMT IHC negative	335	B = 50% of A
expected promoter methylated in tissue	67	C=20% of B and 10% of A
expected with increase of mutational load ≥ 20 mutations/Mb (PRIMING Phase)	20	D= 30% of C

For cohort D, a precise sample size has NOT been calculated since the ORR in deficient patients is a secondary objective of the trial. We will enroll up to 34 MMR-D cases according to an estimated prevalence of 4-5 %. These patients will constitute the **D-cohort**. We expect a response rate between 40% (95% C.I. .18-.71) and 33% (95% C.I. .21-.46) as reported by Le et al., (2015 & 2019) with 11-14 responses accordingly.

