10.3 Statistical Analysis Plan

10.3.1 Populations considered for the analysis

All patients signing the informed consent for the PRIMING and TRIAL Phases will be accounted for. The number of patients who will not result eligible, who died or withdrew before these phases, will be specified.

A patient will be considered to be PRIMING and TRIAL Phases eligible if he/she did not have any deviation from the patient entry criteria listed in section 7.1.2 (PRIMING) and 7.1.3 (TRIAL). Potential eligibility problems will be assessed by the Clinical Study Coordinator at time of medical review.

The final efficacy analysis will occur after 20 patients entered in the P-Cohort are evaluable for response according to RECIST 1.1. The distribution of follow-up time in both cohorts (P and D) will be described and the number of patients lost to follow-up will be reported.

Conclusions will be based on all eligible patients in each cohort. Further analysis may be performed excluding those patients for whom major protocol deviations have been identified (e.g., early death due to other reasons, early discontinuation of treatment, major protocol violations, etc.). However, these sub-analyses may not serve as the basis for drawing conclusions concerning treatment efficacy, and the reasons for excluding patients from the analysis should be clearly reported.

Three populations will be considered for the analysis, as follows:

- The Safety Evaluable (SE) population defined as all treated patients (i.e. eligible as decided at the time of registration that receives at least 1 dose of any study treatment i.e. TMZ and Pembrolizumab). An incorrect treatment schedule or drug administration or an early termination of treatment does not result in exclusion of patients from this population. This population will be the object of the Safety and Tolerability analysis. Patients with major deviations from the eligibility criteria affecting safety or from the treatment schedule at cycle 1 for reasons other than toxicity may be presented in separate tables/listings.
- The Efficacy Evaluable (EE) population defined as all patient treated with pembrolizumab in P-cohort, with no major deviations from the eligibility criteria affecting efficacy evaluation, for which the tumor response could be evaluated at least once while on treatment. These patients should have received at least 2 cycles after treatment starts, unless disease progression occurs within this period.

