- The immunotherapy Efficacy Evaluable (iEE) population. Anti-tumor immune responses such as those associated with pembrolizumab may result in objective responses that are delayed and that can be preceded by initial apparent radiological progression. This initial apparent progression may occur as a result of either delayed anti-tumor activity and/or robust tumor immune cell infiltration with a concomitant increase in tumor size. In addition, lesions that might otherwise be undetectable with conventional imaging may increase in size as a result of these processes and be recorded as new lesions. Conventional RECIST 1.1 response criteria may not be thus adequate to capture and describe the anti-tumor activity of pembrolizumab. Therefore, modified response criteria have been developed that account for the possible appearance of new lesions and allow radiological progression to be confirmed at subsequent assessment. For these reason a second efficacy analysis will be conducted (iEE analysis) on the same population used for the EE analysis using the Modified RECIST criteria.

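### The plan is inconsistent about whether RECIST 1.1 or a RECIST 1.1-then-iRECIST count decides the 5-of-20 test and the 0-of-10 stop

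*Combined protocol and SAP*

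**What the plan says.** **Decision rules (section 10.2, repeated in the synopsis).** Stage 1 enrols 10 patients: "If no responses are observed, the study will be stopped". At the end, "The null hypothesis will be rejected if 5 or more responses are observed in 20 patients". Neither rule says by which criterion a response is counted. The stated type I error is 0.05 at a 10% rate, and the stated power is 90% at 40%.

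**Text pointing to RECIST 1.1.** Section 9.1.3.2 makes RECIST 1.1 the primary measure of tumour response. Section 10.3.1 says that, besides the EE analysis, "a second efficacy analysis will be conducted (iEE analysis") on the same patients with modified RECIST.

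**Text pointing to a combined count.** Section 10.1 places the main analysis on cohort P patients with measurable disease "who have received at least 1 cycle of pembrolizumab (iEE population, see 10.3.1"). Section 10.3.2 defines response as CR or PR assessed "first by RECIST 1.1 and then by iRECIST criteria at the discretion of the local Investigator", and adds: "Best objective response of either type will be centrally confirmed".

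**Text that does not decide.** Section 5.4 says only RECIST and refers to Table 9.1.3, which covers imaging and treatment after first progression and does not define response. Appendix 4 names both criteria for response assessment. Section 10.3.1 says the final analysis "will occur after 20 patients entered in the P-Cohort are evaluable for response according to RECIST 1.1"; that sets timing, not the criterion.

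**Central review and disagreement.** Under 10.3.2 the central evaluation prevails over the local one. Section 9.1.3.1 places central review at trial end. Section 10.3.2 closes with: "Discrepant results, impinging in the acceptance of rejection of the null hypothesis, will be discussed and agreed upon" between the Protocol Chair and the Sponsor.

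**The concern.** This is the only test in the plan with a stated decision rule, and it turns on a count in 20 patients. Two sections support one count and two support another, and the section holding the rule is silent. If the two counts straddle a cut-off, the plan does not say which one governs, and its closing provision allows that to be agreed once the counts are known.

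The ambiguity runs one way. Appendix 4 says there is no separate iRECIST assessment before RECIST 1.1 progression. A combined count therefore contains every RECIST 1.1 responder plus anyone who responds after an apparent progression. It can turn non-rejection into rejection, or a stop into continuation, and not the reverse.

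Central review does not remove the problem. It settles whose reading counts, but it confirms a response of either type, so it does not settle the criterion. It also comes too late for the stage 1 stop.

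**Working it through.** **1. The design's own figures.** Inputs from section 10.2: 10 + 10 patients, continue if at least 1 response in the first 10, reject if at least 5 in 20, null 10%, alternative 40%.

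P(reject) = P(X ≥ 5 | 20, p) − (1 − p)^10 × P(X ≥ 5 | 10, p). The second term removes trials that would have reached 5 but stopped at 0/10.

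- p = 0.10: 0.0432 − 0.3487 × 0.0016 = 0.0426 (stated 0.05)
- p = 0.40: 0.9490 − 0.0060 × 0.3669 = 0.9468 (stated 90%)

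The rule performs slightly better than stated on both counts, so the rule itself is not at issue.

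**2. How often one patient would decide the result.** The critical outcome is exactly 4/20 by RECIST 1.1 with stage 1 passed.

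Joint probability = P(X = 4 | 20, p) − (1 − p)^10 × P(X = 4 | 10, p). Dividing by 1 − (1 − p)^10 gives the probability conditional on passing stage 1.

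| True rate | P(4 of 20) | Term removed | Joint | Conditional |
|---|---|---|---|---|
| 10% | 0.0898 | 0.3487 × 0.0112 | 0.086 | 0.132 |
| 20% | 0.2182 | 0.1074 × 0.0881 | 0.209 | 0.234 |
| 30% | 0.1304 | 0.0282 × 0.2001 | 0.125 | 0.128 |
| 40% | 0.0350 | 0.0060 × 0.2508 | 0.034 | 0.034 |

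**3. Chance that 4/20 becomes at least 5/20.** The documents give no rate of response by iRECIST alone, so a chance q of 1% to 3% per eligible non-responder is assumed. Only patients with RECIST 1.1 progression who are rescanned can qualify. Having 8 eligible is an assumption; all 16 non-responders is the upper case. Formula: 1 − (1 − q)^m.

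| q | m = 8 | m = 16 |
|---|---|---|
| 1% | 0.08 | 0.15 |
| 2% | 0.15 | 0.28 |
| 3% | 0.22 | 0.39 |

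**4. Type I error.** This depends on what the 10% null refers to, which section 10.2 does not say.

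- If it is a RECIST 1.1 rate and iRECIST adds an assumed 1, 2 or 3 points, the combined count has a true rate of 11%, 12% or 13%. The formula in step 1 then gives 0.060, 0.082 or 0.107.
- If it is the rate for the combined count, type I error is 0.0426 and there is no inflation.

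**5. Local read at stage 1, central read at the end.** Stopping can only remove rejections, so with a central rate of 10% the type I error is at most P(X ≥ 5 | 20, 0.10) = 0.0432. With a rate of 40% on both reads, power is at least 0.9490 − 0.0060 = 0.943.

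**The case against.** The best defence is that 10.3.2 is the section on the primary analysis and does define response: RECIST 1.1, then iRECIST, with either type confirmed centrally. Section 10.1 agrees. The word second in 10.3.1 may mean next in order rather than subordinate, and a primary measure in 9.1.3.2 can fit a sequence that begins with RECIST 1.1. The unqualified responses in 10.2 would then take the 10.3.2 definition. This is a plausible reading with real support, and it should not be dismissed. It still sits uneasily with 9.1.3.2 and 10.3.1, and it leaves local discretion inside the response definition.

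A reader might infer that sites may freely opt out of iRECIST when counting responses. The documents do not go that far. The clause in 9.1.3.2 about an investigator not using iRECIST concerns discontinuation of treatment, and the next paragraph but one makes iRECIST re-assessment after RECIST 1.1 progression the default. Some discretion remains, through 10.3.2 itself and because Appendix 4 does not require repeat imaging in clinically unstable patients.

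A reader might also argue that 10.3.3 rules out the combined count, because duration of response ends at first documented progression and an iRECIST-only responder would progress before responding. That is strained: 10.3.2 says duration will be calculated accordingly, and 10.3.3 can be read as progression after response.

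Finally, the sentence on discrepant results follows the local-versus-central text and may concern readers rather than criteria. Even so, it opens to negotiation a disagreement that the preceding sentences had settled by giving the central read precedence.

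**Conclusion.** The concern holds as an inconsistency that must be resolved before responses are counted. The plan supports two different counts for its primary test, names neither in the decision rules, and lets results that affect the null be settled afterwards.

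Its size is the chance that a single patient decides the outcome. On the stage 1-passed, 4/20 outcome the joint probability is at most 0.209 among the four true rates examined. Given 4/20, the chance of reversal is 0.08–0.22 with 8 eligible patients and 0.15–0.39 in the upper case; both ranges rest on assumed iRECIST-only rates of 1–3%.

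It would be too strong to say that the plan inflates its type I error. The 0.060–0.107 range applies only if the null was set for RECIST 1.1 and the assumed increments occur. The finding does not need inflation: the deciding count is unsettled whichever endpoint the null describes. Nor do the documents show that RECIST 1.1 alone was intended; that remains the sponsor's choice.

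**What to change.** Before results are known, and consistently in the synopsis and sections 5.4, 10.1, 10.2, 10.3.1 and 10.3.2:

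- Name one response criterion, either RECIST 1.1 or RECIST 1.1 followed by iRECIST, as one rule for all patients at both stages. Report the other as supportive.
- State that the 10% null and the 40% alternative refer to the named criterion.
- Remove investigator discretion from the response definition.
- Replace the after-the-fact agreement with the rule already in 10.3.2, that the central evaluation decides, and apply it to the final test.
- State that the stage 1 stop uses the local read on the same criterion, and whether those responses must first be confirmed as 9.1.3.1 describes.
- In 5.4 and the synopsis, replace the pointer to Table 9.1.3 with the response definition.

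The cost is text. N = 20, both cut-offs, the scan schedule and the two planned central readers are unchanged. With one read throughout, alpha is 0.0426 and power 0.947; with a local read at stage 1, the bounds in step 5 of the working apply.

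Each choice has a price. If RECIST 1.1 is named, responses after pseudo-progression, which 10.3.1 is concerned to capture, count only in the supportive analysis; and if the combined count was intended, this changes the endpoint rather than the wording. If the sequence with iRECIST is named, the count still depends on whether repeat scans were taken, which central reading cannot remedy.

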Participants who have unconfirmed disease progression may continue on treatment at the discretion of the Investigator until progression is confirmed by the site provided they are clinically stable. Participants who receive confirmatory imaging do not need to undergo the next scheduled tumor imaging if it is less than 4 weeks later; tumor imaging may resume at the subsequent scheduled imaging time point, if clinically stable. Participants who have confirmed disease progression by iRECIST, as assessed by the site, will discontinue study treatment.

- In participants who discontinue study treatment, tumor imaging should be performed at the time of treatment discontinuation (± 4 -week window). If previous imaging was obtained within 4 weeks prior to the date of discontinuation, then imaging at treatment discontinuation is not mandatory. In participants who discontinue study treatment due to documented disease progression, this is the final required tumor imaging.
- In case of discontinuation of treatment for any reason other than disease progression, patients will still be re-evaluated every 8 weeks until disease progression or start of a new treatment or death or patients refusal, whichever comes first.
- After 1 year, the imaging time point will occur approximately every 12 weeks.
- At trial end, all in-Trial tumor assessments radioimaging data will be reviewed centrally by two radiologists who will read the CT/MRI scans blinded using the Quibim Precision[®] software to collect, store, and guide the revision of the imaging results. The imaging review protocol and tumor assessment reconciliation report will be included in the final study report and or in the publication of the study.

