9.1.3.2 Disease assessment

RECIST 1.1 (referencing a maximum of 5 target lesions in total and 2 per organ) will be used as a primary measure for assessment of tumor response and as date of disease progression.

The Sponsor might also require, for research purpose, to enable a broader sampling of tumor burden to be conducted centrally.

RECIST 1.1 Progression (PD) definition will be used for discontinuation of study treatment during the temozolomide PRIMING phase, and in TRIAL phase whenever the Investigator at site decide NOT to use iRECIST criteria, as described below. iRECIST is based on RECIST 1.1, but adapted to account for the unique tumor response seen with immunotherapeutic drugs.

Disease assessment in the TRIAL phase for both Cohorts takes into account the observation that some patients treated with immunotherapy can have a transient tumor flare, which might be misconstrued for PD by RECISTs, in the first few months after the start of pembrolizumab, and then experience subsequent disease response. Thus in the TRIAL phase, when tumor imaging shows PD by RECIST 1.1 the local investigator will re-assess the patient per iRECIST criteria according to the flow-chart in figure 9.1.3, table 9.1.3.

Per iRECIST, disease progression should be confirmed by the site 4 to 8 weeks after first radiologic evidence of RECIST 1.1 PD in clinically stable participants. Participants who have unconfirmed disease progression may continue on treatment at the discretion of the Investigator until progression is confirmed provided they have met the conditions detailed in Table 9.1.3 below.

Patients who receive confirmatory imaging do not need to undergo the next scheduled tumor imaging if it is less than 4 weeks later; tumor imaging may resume at the subsequent scheduled imaging time point, if clinically stable. Participants who have confirmed disease progression by iRECIST, as assessed by the site, will discontinue study treatment. Exceptions are detailed in table 9.1.3.

[figure not shown]
A description of the adaptations and iRECIST process is provided in Appendix 4, with additional detail in the iRECIST publication (Seymour et al., 2017).

Table 9.1.3: Imaging and Treatment after First Radiologic Evidence of Progressive Disease

	Clinically Stable		Clinically Unstable	
	Imaging	Treatment	Imaging	Treatment
Imaging and treatment options at first RECIST PD determination				

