9.1.7.4.2 Follow-up Visits

Participants who discontinue study treatment for a reason other than disease progression will move into the Follow-Up Phase and should be assessed every 8 weeks (56 ± 7 days) by radiologic imaging to monitor disease status. After 1 year, the imaging time point will occur every 12 weeks (± 7 days). Every effort should be made to collect information regarding disease status until the start of new anti-cancer therapy, disease progression, death, end of the study or if the participant begins retreatment with pembrolizumab as detailed in section 7.3.5.

Information regarding post-study anti-cancer treatment will be collected if new treatment is initiated.

Participants who are eligible to receive retreatment with pembrolizumab according to the criteria in section 7.3.5 will move from the follow-up phase to the Second Course Phase when they experience disease progression.

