10.3.3 Secondary analyses

A secondary analysis will also estimate the ORR, as defined above, in the D-Cohort and compare it to the ORR in the P-cohort. CIs for the difference in ORRs between the two cohorts

will be determined using the normal approximation to the binomial distribution. The ORRs will be compared between the two cohorts with use of the stratified Cochran-Mantel-Haenszel test.

PFS and OS, for both cohorts, will be estimated using the Kaplan-Meier product-limit method. Estimates at weekly intervals will be tabulated with their standard error; medians will be provided with 95% confidence interval.

DCR is defined as the rate of patients with complete or partial response as best response or stable disease maintained for ≥ 18 weeks per RECIST v1.1. The analysis methods for DCR will be the same as those for the analysis of ORR.

Duration of response, defined as the time between the date of the first occurrence of a complete or partial response and the date of first documented progressive disease or death is documented, will also be estimated using Kaplan-Meier methodology above. Patients who have not progressed or who have not died by the data cutoff date for analysis will be censored at the time of last tumor assessment date. If no tumor assessments were performed after date of the first occurrence of a complete or partial response, DOR will be censored at the date of the first occurrence of a complete or partial response plus 1 day.

Adverse events will reported as proportions.

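### If duration of response follows the central read, a site progression that the central readers do not confirm lengthens it, because imaging has already stopped

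*Combined protocol and SAP*

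**What the plan says.** Section 10.3.2 has best objective response confirmed centrally and then states that, when the local and central evaluations disagree, "the central response evaluation will be used for the analysis. The duration of response will be calculated accordingly".

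The timing of the central review is in Section 9.1.3.1: "At trial end, all in-Trial tumor assessments radioimaging data will be reviewed centrally by two radiologists". The same section sets the end of imaging: "In participants who discontinue study treatment due to documented disease progression, this is the final required tumor imaging". Scans after treatment are for the others (Section 9.1.7.4.2): "Participants who discontinue study treatment for a reason other than disease progression will move into the Follow-Up Phase". After confirmed progression, follow-up is a telephone contact every 12 weeks for survival (Section 9.1.7.4.3).

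Section 10.3.3 runs DOR from first response to first documented progression or death. Patients with neither by the data cutoff "will be censored at the time of last tumor assessment date". It does not say whose reading documents the progression. Section 9.1.3.2 says that RECIST 1.1 "will be used as a primary measure for assessment of tumor response and as date of disease progression", again without naming a reader.

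**The concern.** These rules fit together badly. The site's call of progression ends treatment and required imaging. The central readers see the scans only afterwards and cannot ask for more. If they do not call progression on the last available scan, the central progression date can no longer be observed, and no rule covers that patient.

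Kaplan-Meier assumes that a patient censored at a given time would have gone on like those still followed. Here censoring is triggered by a scan that the site judged to show progression, so it is informative. Where the patient dies before cutoff, the event is recorded, but at death rather than at progression. Both routes lengthen DOR relative to a central DOR with complete imaging.

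At stake is a descriptive result in few patients, which readers will set beside the response rate. In addition, because neither Section 9.1.3.2 nor Section 10.3.3 names a reader, the DOR and PFS progression dates of one patient could come from different reads.

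**Working it through.** **1. The plan's figure.** Section 10.2 expects 11-14 responses in cohort D: 34 × 0.33 = 11.2 and 34 × 0.40 = 13.6. This reproduces. It is the only stated expected responder count that bears on the size of a DOR analysis. The documents give no DOR assumption and no local/central discordance rate.

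**2. Precision.** At a true rate of 50% and without censoring, SE = √(0.25/n): √(0.25/14) = 13.4 points and √(0.25/11) = 15.1 points. Half an SE is 6.7 to 7.5 points.

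**3. When imaging ends.** A clinically stable patient is re-scanned 4 to 8 weeks after first RECIST 1.1 progression (Section 9.1.3.2, Table 9.1.3), so required imaging usually ends at confirmed site progression. It ends at first progression if the patient is clinically unstable or the investigator does not use iRECIST.

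**4. Simulated bias.** Inputs from the plan: 9-week scans (Section 9.1.3.1) and a 36-month trial (Section 2.0). Assumptions: exponential DOR with median 6 or 12 months; a share f = 10, 20 or 30% of progressions called by the site only; central progression 1 or 2 scans later had imaging continued; median survival after progression 4, 8 or 12 months; responses starting evenly over the first 24 months; no extra confirmatory scan. Each scenario had 40,000 responders. Three Kaplan-Meier rates at 12 months were compared:

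- Target: central read, imaging continued.
- As written, if the central read sets the date: a site-only progression is an event at death if death precedes cutoff, and otherwise is censored at that scan.
- Site progression counted as the event on its scan date.

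| Median DOR (months) | f | Survival after PD (months) | Scans later | Target | As written | Difference (points) | Site PD as event |
|---|---|---|---|---|---|---|---|
| 12 | 10% | 4 | 2 | 56.0% | 56.7% | +0.7 | 55.0% |
| 12 | 20% | 4 | 1 | 56.3% | 58.6% | +2.3 | 55.2% |
| 12 | 20% | 8 | 1 | 56.4% | 60.2% | +3.8 | 55.1% |
| 12 | 20% | 12 | 1 | 56.3% | 60.7% | +4.4 | 55.0% |
| 12 | 20% | 12 | 2 | 57.4% | 60.5% | +3.1 | 54.9% |
| 6 | 30% | 12 | 1 | 33.0% | 42.7% | +9.7 | 30.7% |

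The first and last rows are the smallest and largest differences over all scenarios, so the overstatement is about 1 to 10 points and never negative. Between 13% and 48% of site-only progressions end up censored; the rest become events at death.

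**5. Landmark.** Twelve months falls between the week-45 and week-54 scans. Read at week 54, with a 12-month median, f = 20% and survival after progression of 6-12 months, the target is about 50-51% and the rule as written about 54-55%. The shift is about 3 to 5 points, and about 4 to 5 when central progression would have come one scan later.

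**6. The alternative run.** Counting the site progression as the event falls below the target by about 0.5 points (12-month median, f = 10%: 55.7% against 55.2%) to about 5 points (6-month median, f = 30%, two scans later: 35.3% against 30.7%). The two versions therefore bracket the target.

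**The case against.** The strongest objection is that the premise is inferred. The override in Section 10.3.2 follows a sentence about best objective response, and Section 10.3.3 speaks only of documented progression, which a site progression could satisfy. On that reading the bias does not arise. This stands as a limit: the point holds only if the central read governs the progression date. It does not remove the point, because the sentence on DOR makes that reading natural and nothing excludes it.

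A reader might infer that imaging stops at first site progression and that every unconfirmed case is censored. The documents do not support either. Stable patients are re-scanned, which should lower discordance by an amount that cannot be computed. Deaths before cutoff are DOR events.

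A reader might also infer a larger shift. If every site-only progression were censored, the hazard would fall by f, and at f = 20% a true 50% would become 0.5^0.8 = 57.4%, or 7.4 points. That calculation ignores deaths and compares with the site-read DOR, when the proper target is the longer central DOR. The 3 to 5 points in step 5 are below half an SE.

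Nor can a size be put on PFS: the censoring sentence in Section 10.3.3 belongs to DOR, and no reader or censoring rule is given for PFS.

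Two further objections carry weight. Section 9.1.3.1 already promises a reconciliation report on tumor assessments, so discordance is partly covered. And making an unconfirmed site progression the main event would shorten DOR whenever the central readers were right, which is why it belongs in a sensitivity analysis.

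**Conclusion.** The gap is real and its direction is upward, provided the central read sets the progression date. Under the assumptions in the working, the 12-month DOR rate is overstated by about 1 to 10 points. With a 12-month median and f = 20%, the shift is about 4 to 5 points at week 54 when survival after progression is 6-12 months and central progression would have come one scan later; it is smaller with shorter survival or a longer lag. With 11-14 responders the SE is 13-15 points, so only the upper part of the range exceeds half an SE.

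The size rests on assumed discordance and survival. The 4-8 week confirmatory scan would reduce it. An early cutoff would raise the share censored, and Section 10.3.1 ties the final efficacy analysis to 20 cohort P patients being evaluable for response, not to DOR follow-up.

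The consequence is limited. The response-rate test in cohort P is untouched, and DOR is not among the endpoints in Sections 5.4 to 5.6, although Sections 10.3.2 and 10.3.3 commit to reporting it. The remedy is cheap enough to be worth making.

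**What to change.** Amend Sections 10.3.2 and 10.3.3 before the central reads begin, so that the choice cannot depend on the results:

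- State which reader sets the progression date, and use the same source for DOR and PFS.
- Keep the central DOR. Beside it, report a prespecified sensitivity analysis in which a site progression that ended treatment and imaging, with no later centrally read scan, is an event on that scan's date.
- Report the number of responders with a site-only progression, and how many of them were censored or counted at death. The planned reconciliation report is a natural place.

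The cost is a few sentences in the SAP and one extra run, with no extra scans. The downside is a somewhat shorter DOR shown beside the central one, and a mixed-reader definition to explain.
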